1.4 Preliminary Data

The PI is a co-founder of the CHAMPIONS NETWork program for high school students in underserved Chicago neighborhoods. Youth are trained as health advocates and then act as health educators for ED patients and family members at home. Youth participants have shown significant increases in empowerment and health knowledge.²⁸ In 2017, the CHAMPIONS NETWork received funding to implement a cardiovascular health digital badge, where youth learned and educated adult family members about cardiovascular health. After completion, youth focus groups indicated their overall positive response to the experience, and appreciation of the badge's active learning and its long-term benefits.⁴¹ However, any impact of the health education provided by the students on health changes for the adult was not measured and is currently unknown. This study builds upon this work to implement a youth-led digital health education intervention to improve hypertension (HTN) disparities in adult ED patients.

1.5 Sample Size Justification

This is a pilot study. All sample sizes for this study will provide adequate initial information for the development, effectiveness, and implementation metrics on this novel intervention. Future larger studies on the intervention will include a sample size calculation to determine appropriate sample for appropriate power to fully test the intervention.

1.6 Study Variables

A. Independent Variables, Interventions, or Predictor Variables

Aim 1: Not applicable

Aim 1a: Not applicable

Aim 2: For the first cohort, outcomes will be compared for dyads randomized to the intervention arm versus those randomized to the control arm, where youth participants in the intervention arm will complete the youth-led HTN education digital badge with their hypertensive adult and youth participants in the control arm will complete job readiness digital badge(s).

For the school cohort, we will be looking at changes before and after the 6-week intervention in adult and youth participants.

Aim 3: Not applicable

B. Dependent Variables or Outcome Measures

Aim 1: Not applicable

Aim 1a: Not applicable

Aim 2: For the first cohort, the primary outcome is change in BP (in mm Hg) from baseline to 1 week and 2 months later. We will also collect secondary outcomes of pre- and post-intervention change in HTN knowledge, adult BP self-care, adult self-efficacy to manage HTN and youth confidence in managing adult BP during the same timepoints.

For the school cohort, outcomes of interest are HTN knowledge, confidence in HTN management, and health behavior changes in participants. (Same outcomes as the first cohort except for the BP change.)

Aim 3: Not applicable

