1.0 Research Design

1.1 Purpose/Specific Aims

The proposed study will integrate user-centered design, community engagement, and implementation science, with a randomized controlled trial (RCT), to develop, test, and collect implementation data on a youth-led HTN education digital badge. The badge will act as an electronic tool to guide youth through learning and then teaching adults on how to achieve better HTN control. Adults with HTN and youth from the local community will be recruited for user-centered design sessions to provide input in the development of a youth-led HTN education digital badge. We will then recruit adult ED patients with uncontrolled HTN (BP $\geq 130/80$ mm Hg) who have an existing relationship (such as family member) with a youth (14-24 years old) and the youth themselves for an RCT. The adult plus youth dyad will be randomized to either: 1) intervention arm- 6-week youth-led HTN education digital badge at home- or 2) control arm- 6-week youth job readiness digital badge at home. In addition to the primary study outcome of adult BP change 2-months post-intervention, we will collect secondary outcomes of HTN knowledge and youth self-efficacy, as well as implementation metrics of intervention acceptability, feasibility, and fidelity. Bringing health education to the patient's home, while simultaneously empowering youth is an innovative technology-driven model for improving BP for patients with uncontrolled HTN who may lack access to care. Outcomes of this project will result in a scalable and easily adoptable model to empower youth while simultaneously improving BP in a difficult to reach adult population.

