Due to challenges recruiting youth through adults in the ED, we will be adding a cohort to the study. For this new cohort of the study, we will recruit interested youth from New Brunswick Health Sciences Technology High School (NBHSTHS). Students will be asked to pair themselves with an adult (18+) (preference for adult who has been diagnosed with hypertension, but not mandatory) with an existing relationship with the student where it would be feasible to complete an online module together 1 hour per week for 6 weeks. The adult must be fluent in English or Spanish and the student must be able to speak the fluent language of the adult. We will evaluate the youth-led digital hypertension (HTN) education intervention- an electronic tool to guide youth through learning and then teaching and supporting adults on how to control hypertension (for adults with hypertension) and how to avoid it (for adults without hypertension). Outcomes of interest are HTN knowledge, confidence in HTN management, and health behavior changes in participants, which will be obtained through pre- and post- intervention assessments. We will also be exploring outcomes of participant acceptability, feasibility, and fidelity of the intervention.

A. Objectives

Specific aims are:

Aim 1: Create a youth-led HTN education digital badge by means of user-centered design methods and community engagement with adults with HTN and youth to obtain input on the contents of the digital badge prior to implementation.

Aim 1a: The hypertension knowledge assessment being used in the study has not been used before on youth or Spanish-speaking populations, so we will obtain feedback on the assessment from these groups.

Aim 2: Evaluate the effectiveness of a youth-led HTN education digital badge intervention on the primary outcome of mean systolic BP (SBP) and diastolic BP (DBP) change in adults with uncontrolled HTN at 2-months post-intervention compared to the control group. Additionally, evaluate change in HTN knowledge and youth self-efficacy. Additionally, we will measure confidence in HTN management, and health behavior changes in participants.

Aim 3: Evaluate the implementation process of the youth-led HTN education digital badge by collecting qualitative and quantitative data on acceptability, feasibility, and fidelity of the intervention by participants.

B. Hypotheses / Research Question(s)

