Research Question (Aim 1): *What are the most acceptable and easily understood ways to present HTN information to this population?*

Hypothesis 2abc (Aim 2): (a) The mean SBP and DBP differences at 2-month post-intervention will show greater decreases for the intervention group than the control group. (b) HTN knowledge will increase from pre- to post-intervention in youth and adults in the intervention group and will not change in control group. (c) Youth self-efficacy will increase from the pre- to the post-intervention period in both the intervention and control groups.

Hypothesis 3 (Aim 3): *The intervention will overall have high acceptability and feasibility (average scores of ≥ 4 on the Acceptability of Intervention Measure (AIM) and Feasibility of Intervention Measure (FIM) scales¹) and fidelity (majority will complete entire digital badge playlist correctly).*

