Arm 1- Intervention: Participants in the intervention arm will receive the youth-led HTN education digital badge to complete, which will be comprised of a 6-week playlist of one module per week comprising the playlist. Youth will learn from the module and will teach the adult in their dyad about hypertension education in each week's themed module.

Arm 2- Control: For dyads that are randomized into the control arm, the youth will complete job readiness digital badges. These will include a Career & Job Readiness digital badge playlist, with such playlists as, "Interview Preparation", "Resume Ready", and "Professionalism". While this group may complete multiple digital badges, the total time needed to complete the badges will be approximately equivalent to that of the intervention group (eg. one hour per week for each arm).
9. For both arms, youth must submit evidence of completion (eg. photograph, document) as specified in the playlist's instructions. Evidence will be reviewed by the study team and a digital badge is received if all XPs are satisfactorily completed. If not satisfactorily completed, then a note will be sent back to the youth on how to fix or improve the evidence and resubmit.

10. Adult participants in both arms return to RWJUH for follow-up BP check and complete follow-up assessments- blood pressure self-care scale, hypertension knowledge assessment, and self-efficacy to manage hypertension scale. They will receive an incentive for returning at 1 week and 2 months after completion of digital badge. Youth will complete follow-up assessments of hypertension knowledge and confidence in managing blood pressure of adults at the same timepoints but will be done remotely/electronically.

Due to challenges recruiting youth through adults in the ED, we will be adding a cohort to the study. For this new cohort of the study, we will recruit interested youth from NBHSTHS. Students will be asked to pair themselves with an adult (18+) (preference for adult who has been diagnosed with hypertension) with an existing relationship with the student where it would be feasible to complete an online module together 1 hour per week for 6 weeks. The adult must be fluent in English or Spanish and the student must be able to speak the fluent language of the adult. For this cohort, study procedures are as follows:

1. We will recruit students at NBHSTHS for information sessions (see youth recruitment flyer).

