Questionnaire: At the conclusion of each hypertension education module in the intervention, all participants in the intervention group will be asked to complete a questionnaire on the intervention's acceptability and feasibility as part of the requirement for module completion. Participants must complete the questionnaires to receive their study incentive.

Interviews: We will also conduct one-on-one phone interviews with interested participants from the intervention group for more in-depth information on intervention acceptability, feasibility, and fidelity. These will take place halfway through the intervention and at the end of the intervention. Interviews will be available in English and Spanish, and be audio recorded.

B. Data Points

Aim 1 (Group 1): Participation will be a one-time design session that will take place prior to the start of the RCT.

Aim 1a: Participation will be a one-time cognitive interview session.

Aim 2 (Group 2): For the first cohort, BP will be collected at baseline in the ED and at 1 week and 2-month post-intervention follow-ups at RWJUH. Pre- and post-intervention change in HTN knowledge, adult BP self-care, adult self-efficacy to manage HTN and youth confidence in managing adult BP will be collected during the same timepoints.

For the school cohort, youth and adult participants will complete study assessments after consent is signed. Fidelity of the intervention will be collected on youth the following week, and youth will complete a HTN knowledge assessment at the end of this session. At the end of each of the 6 intervention modules, participants will complete module feedback assessments. At the end of the 6 week intervention and then 1 month after the end of the 6 week intervention, all participants will complete study assessments.

Aim 3 (Group 2): Implementation data points will be collected at the end of each module (surveys) and at the midpoint and end of the intervention period (6 weeks post-baseline) (interviews).

C. Study Duration

Aim 1 (Group 1): Participation will be a one-time design session that will last approximately 1.5 hours.

The duration of this aim is expected to be about 3 months.

Aim 1a: Participation will be a one-time cognitive interview session that will last approximately 30 minutes. The duration of this aim is expected to be about 3 months.

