Aim 2 (Group 2): For the first cohort, participation duration will be 3.5 months (6 weeks for digital badge intervention plus 2 months for final follow-up after completion of intervention). Baseline data collection is expected to take approximately 20 minutes. During the 6-week digital badge intervention, participants will spend approximately 1 hour per week on the digital badge. Follow-up data collection is expected to take approximately 20 minutes per session (with sessions at 1 week and 2 months).

For the school cohort, youth participation duration will be 12 weeks (about 3 months) (2 weeks for training, 6 weeks for digital badge intervention plus 4 weeks for final follow-up after completion of intervention). Two training sessions at weeks 1 and 2 are expected to take about 40-60 minutes each. Baseline data collection is expected to take approximately 20 minutes. During the 6-week digital education module, participants will spend approximately 1 hour per week on the module. Follow-up data collection is expected to take approximately 20 minutes per session (with sessions at 8 week and 12 weeks).

Adult participation duration will be 10 weeks (6 weeks for digital badge intervention plus 4 weeks for final follow-up after completion of intervention). Baseline data collection is expected to take approximately 20 minutes. During the 6-week digital education module, participants will spend approximately 1 hour per week on the module. Follow-up data collection is expected to take approximately 20 minutes per session (with sessions at the end of the intervention and 1 month later).

Aim 3 (Group 2): The quantitative implementation data questionnaire is expected to take approximately 5-10 minutes to complete. The qualitative interviews will last approximately 30-45 minutes each.

The duration of Aims 2 and 3 are expected to be 1.5 years total for the study.

D. Endpoints

Aim 1: Participation will be a one-time design session that will last approximately 1.5 hours.

Aim 1a: Participation will be a one-time cognitive interview session that will last approximately 30 minutes.

Aims 2 and 3: For the first cohort, participation ends 2 months after the end of the 6-week intervention (3.5 months after baseline). For the school cohort, participation ends after 12 weeks for youth and after 10 weeks for adults.

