Aim 2: For the first cohort, BP data will be collected when the potential participant is in the ED by the recruiter- either the RA or PI and will be entered into the RedCap study database. It will then be collected at 1 week and 2 months post-intervention when the adult participant returns to RWJUH for follow-up BP readings which will be entered into RedCap. HTN knowledge, self-efficacy, and self-care data will be collected electronically via RedCap. Participants will be sent a link to the appropriate questionnaires to be completed at baseline, 1 week post intervention, and 2 months post intervention.

For the school cohort, data collection will be done through Redcap. Questionnaires will be completed in person at the school (youth) or remotely (adults).

Aim 3: All participants in the intervention group will be asked to complete a questionnaire at the end of each intervention module through the digital badge platform, which will allow them to complete the questionnaire in RedCap. Participants must complete the questionnaires to receive their digital badge incentive.

We will also conduct one-on-one phone/Zoom interviews with interested participants for more in-depth information on intervention acceptability, feasibility, and fidelity. Interviews will last approximately 30-45 minutes each, be available in English and Spanish, and be audio recorded. The audio recording will then be transcribed by the RA.

▪ **Timing and Frequency:**

Aim 1: Participation will be a one-time design session.

Aim 1a: Participation will be a one-time design session.

Aim 2: For the first cohort, BP will be collected at baseline in the ED and at 1 week and 2-month post-intervention follow-ups at RWJUH. HTN knowledge, self-care, and self-efficacy will be collected at the start of the intervention, and at 1 week and 2 months post-intervention.

For the school cohort, youth and adult participants will complete study assessments after consent is signed. Fidelity of the intervention will be collected on youth the following week, and

youth will complete a HTN knowledge assessment at the end of this session. At the end of each of the 6 intervention modules, participants will complete module feedback assessments. At the end of the 6-week intervention and then 1 month after the end of the 6-week intervention, all participants will complete study assessments.

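### Section 1.6B makes a 1-week BP change co-primary with no analysis behind it, and Section 6.1 names no primary analysis and picks covariates by baseline significance tests

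*Combined protocol and SAP*

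**What the plan says.** Section 1.6B, on the ED cohort: "the primary outcome is change in BP (in mm Hg) from baseline to 1 week and 2 months later".

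Three statements in Section 1.1 name only the later visit. The opening refers to "the primary study outcome of adult BP change 2-months post-intervention". Aim 2 gives the "primary outcome of mean systolic BP (SBP) and diastolic BP (DBP) change in adults with uncontrolled HTN at 2-months post-intervention". Hypothesis 2a reads "The mean SBP and DBP differences at 2-month post-intervention will show greater decreases for the intervention group than the control group".

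The visit schedule in Section 1.3 B is "BP will be collected at baseline in the ED and at 1 week and 2-month post-intervention follow-ups at RWJUH".

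Section 6.1 (Aim 2) plans three things:
- t-tests and chi-square tests to judge whether characteristics are balanced between arms;
- a t-test on how far mean BP has moved between baseline and the 2-month visit;
- a linear regression comparing the arms, with terms for arm, baseline BP and whichever covariates turned out to be unbalanced.

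Neither BP analysis is called primary. No candidate covariates and no threshold for imbalance are listed. There is no alpha level and no rule for SBP and DBP together. Section 1.5 calls the study a pilot and leaves power calculations to later trials. Section 4.3 gives 100 dyads for Aim 2.

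**The concern.** A reader who takes the primary outcome from Section 1.6B finds two visits. A reader who takes it from Section 1.1 finds one. The 1-week change is called primary in one place and analysed nowhere. At the chosen visit, Aim 2 could then be answered by the t-test or by the regression, and the regression cannot be written down until the baseline tests have been run. With SBP and DBP both named, even a single visit and a single model leave two results and no rule for combining them.

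What is at stake is mainly the effect estimate that the pilot hands to a larger trial. It should come from one visit and one model, both fixed before the outcomes are seen. A false-positive question arises only if either BP component alone may be taken as success.

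**Working it through.** The plan has no figure to reproduce: alpha, SD, effect size and dropout are not stated. The first two steps compare text. The last two are illustrations on stated assumptions.

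**1. Which visit is primary**

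| Place | Visit |
|---|---|
| 1.6B, outcome definition | 1 week and 2 months |
| 1.1, opening | 2 months |
| 1.1, Aim 2 | 2 months, SBP and DBP |
| 1.1, Hypothesis 2a | 2 months, SBP and DBP, between arms |
| 6.1, t-test | 2 months |
| 6.1, regression | none named; 2 months if read with the sentence before it |

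Section 1.6B is the single outlier. No row supplies an analysis of the 1-week BP change.

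**2. Where the clock starts**

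Section 1.6B counts its visits from baseline. Section 1.3 A, step 10, has adults "returning at 1 week and 2 months after completion of digital badge", and Section 1.9 says of BP: "It will then be collected at 1 week and 2 months post-intervention when the adult participant returns to RWJUH". The sentence in 1.6B that follows the definition places the secondary outcomes before and after the intervention, at the same visits. So the visits themselves are fixed, and the wording of 1.6B is loose.

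**3. The covariate rule**

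Assumed: all 100 dyads are in the randomised cohort and split evenly (50 per arm); six candidate covariates, each correlated 0.3 with 2-month BP; a covariate enters if its baseline test gives p<0.05; no true effect.

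- Type I error with test-selected covariates: 3.7-4.5% over four sets of correlations, 6,000 simulated trials each.
- Type I error with arm and baseline BP only: 4.4-5.3% in the same trials.
- A separate run of 2,000 trials per scenario gave 3.9% with selection. The SD of the estimated arm effect, in outcome SD units, was 0.19 with selection and 0.14 with all six covariates fixed in advance. The ratio is 0.19/0.14 = 1.36.

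The rule is therefore slightly conservative and loses precision, because it usually leaves out covariates that predict the outcome. The loss would be smaller if the covariates overlapped or were weaker predictors.

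**4. SBP and DBP at 2 months**

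Assumed: two-sided 0.05 per test; one baseline-adjusted regression per component; SBP-DBP correlation 0.5-0.7; baseline to 2-month correlation 0.3-0.5; baseline SD 0.7-1.0 of follow-up SD; 20,000 null trials per scenario.

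- If the two tests were independent: 1 - (1 - 0.05)² = 9.75%.
- Either component significant, 50 per arm: 8.1-9.3% in either direction, and 4.0-4.7% in favour of the badge (a single test gives 2.5%).
- The same at 25 per arm: 7.9-9.5% and 4.1-4.7%.
- Both components required: 0.8-1.7% in either direction, at both arm sizes.
- Joint power when both are required (bivariate normal): 80% per component becomes 68.7% at correlation 0.5 and 71.3% at 0.7; 50% becomes 33.3% and 37.3%.

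**The case against.** The best defence is that the intent is clear. All of Section 1.1 and the t-test in Section 6.1 point to 2 months, so 1.6B can be aligned in one line. Covariates are chosen from baseline data, not from outcomes, and no error inflation follows. Hypothesis 2a joins SBP and DBP with a plain conjunction, which can be read as requiring both. The study is a pilot and states no rule for declaring success. All of this stands, and it limits the weight of the point. It does not supply a primary analysis, a covariate list or an SBP/DBP rule.

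Four stronger inferences are tempting, and the documents do not support them:

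- *BP will be measured 1 week and 2 months after baseline.* Sections 1.3 and 1.9 consistently place the visits after the badge. This is a wording slip and not a separate defect.
- *The t-test is run within each arm, so it cannot test Hypothesis 2a.* The phrase in 6.1 is loose. But 1.6A says that outcomes are compared between randomised arms, Aim 2 compares with the control group, and 6.1 introduces the regression as a further comparison. A between-arm test is the more natural reading.
- *Chance imbalance makes the analysis invalid.* With 5 to 10 independent baseline tests at 0.05, at least one is significant in 23-40% of trials (1 - 0.95^5 and 1 - 0.95^10). That is how often a covariate would be flagged, not an error rate for the treatment comparison.
- *Two visits, two components and two models make eight chances of success.* The plan has no 1-week BP analysis and never says that any one result is enough.

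**Conclusion.** The point holds in limited form. Section 1.6B conflicts with the rest of the plan on the primary visit, and the 1-week change has no analysis. Section 6.1 does not name a primary analysis and lets baseline tests choose the model. The joint reading of SBP and DBP is open.

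The covariate rule costs precision, not validity: in the illustration, about 4% type I error and an estimate whose SD is about 1.36 times that of the pre-specified model. The SBP/DBP gap matters for error only if either component may count, when the rate is about 8-10%. These rates say nothing about the 1-week question, which is purely one of definition.

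The alpha level, arm sizes, correlations and number of covariates are assumptions. The documents also do not say how the 100 dyads divide between the ED and school cohorts. For a pilot this should be fixed, but it does not undermine the trial.

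**What to change.** 1. In 1.6B, make the change in BP from baseline to 2 months after the end of the intervention primary, and the change to 1 week after it secondary. This also removes the loose timing.
2. In 6.1, name as primary the between-arm linear regression of 2-month BP on arm and baseline BP, reported as an estimate with a 95% CI. (With baseline BP in the model, using change as the response gives the same arm coefficient.) List any further covariates before outcome data are examined, on prognostic grounds, and drop baseline significance tests as the selection rule.
3. State that the t-test is a supportive between-arm comparison of change.
4. Before outcome data are examined, state how SBP and DBP are read together. The choice closest to Hypothesis 2a is to require both, which needs no alpha adjustment. The alternatives are one named primary component, or either component with a multiplicity procedure such as Holm or a fixed sequence.

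Cost: a protocol wording change in 1.6B and 6.1 and a sentence in 1.1, with no new visits, data or participants. Because Section 1.1 shows that ED recruitment has already begun, it would be a mid-study amendment and must precede any look at outcomes. The 1-week result becomes secondary. Requiring both components lowers power, for example from 80% each to about 69-71% jointly.
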